Study Protocol and Statistical Analysis Plan
For Research Project:
“Safety and Efficacy of Combining Intranasal Insulin & Acute Exercise”

clinicaltrials.gov # NCT04292535

conducted by [name], Ph.D.

March 19, 2021

“Safety and Efficacy of Combining Intranasal Insulin & Acute Exercise”

Abstract: To determine if physical activity engagement alters the dose-response profile and safety of administration of insulin into the intranasal mucosa. Using a randomized placebo controlled double-blind pre-posttest design, participants were randomly assigned to receive a dose of either 0, 20, 40, 60, 80, 100, or 120 IU of NovoLog insulin aspart prior to being randomized into participating in a 20 minute session of either moderate-intensity aerobic exercise or a passive control condition. The safety of the protocol was assessed using a symptom questionnaire assessing common symptoms of altered blood glucose and common side effects of intranasal insulin. The efficacy of the intranasal insulin for inducing alterations in cognition was assessed using both behavioral and neuroelectric measures.

Aims:

- 1) To provide a preliminary assessment of the safety profile of combining intranasal insulin with exercise; to ensure that undue risks are not incurred through combination therapeutic approaches.
- 2) To provide a preliminary assessment of the efficacy of combining intranasal insulin with exercise for enhancing inhibitory aspects of cognitive control and sustained attention alongside neuroelectric indices of attention.

Design: Double blind, placebo controlled Phase 2 clinical trial using serial stratification randomization accounting for biological sex. Participants were first allocated to a dose of intranasal insulin (0 [placebo], 20, 40, 60, 80, 100, 120 IU), then allocated to either exercise or control activity.

Study Population: Given the potential risk of combining exercise with intranasal insulin the present investigation utilized a sample of healthy, non-diabetic, fasted college-aged adults to limit the potential for a serious adverse event. The sample consisted of college aged young adults from the mid-Michigan, USA area.

Eligibility Criteria:

Criteria for inclusion: All individuals that agreed to participate were selected on a first come, first serve basis. No individual was turned down due to sex, race, or ethnicity. The following inclusion criteria exist for all participants:

- a. Participants must be over the age of 18.

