Assessment day (day 2): See Figure 1 for an overview of the assessment activities.

[figure not shown]

Figure 1. Diagram of experimental protocol.

Upon arriving to start the second day of testing, participants' blood glucose level was assessed via a glucometer (CVS Health Advanced Blood Glucose Meter, United States) to ensure that their blood glucose fell within the 70-115 mg/dL guideline to exercise safely. Following this, participants were outfitted with a polar heart rate monitor (Model H7, Polar Electro, Finland) to assess heart rate during the experimental condition and then were prepared for neuroelectric testing. Participants were subsequently seated in a sound-attenuated testing chamber approximately 1 m away from the computer monitor where they completed tests of inhibitory control and sustained attention while behavioral and neuroelectric measures were assessed. Once the pretest cognitive assessment was completed, participants were administered solution into their intranasal mucosa.

Using a double-blind, placebo-controlled approach; identical vials of saline solution and Novolog insulin aspart 100 mg/mL were obtained differentiated only by the color of the stopper top, and labeled as investigational drug A and investigational drug B. All participants were administered 6 doses of 0.2 mL of solution via the LMA MAD Nasal Intranasal Mucosal Atomization device into alternating nostrils with a total administration volume of 1.2 mL. The dose of intranasal insulin was controlled by varying the number of doses which contained saline relative to the doses which contained Novolog insulin aspart 100 mg/mL (see Figure 2). The experimenters were aware of the number of doses of investigational drug A and investigational drug B administered; but were unaware which solution or stopper top was associated with insulin or saline. Following administration of the solution, participants completed the sitting/exercise experimental conditions.

Figure 2. Illustration of the intranasal insulin dosing protocol.

Active Comparator: Passive Control. The sitting experimental condition consisted of a 20 min duration where participants sat in a chair (HR = 73.2 bpm [95% CI: 70.3 to 76.2]).

Intervention. The exercise experimental condition consisted of similar 20 min duration of exercise on a motor-driven treadmill at an intensity between 60 and 65% of maximum heart rate achieved during the test of maximal oxygen uptake (HR = 118.1 bpm [95% CI: 116.2 to 120.1]).

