During both the sitting and exercise experimental conditions, participants watched an emotionally neutral video (minutes 65-85 from Wonders of the Universe (*Wonders of the Universe*, 2011)). Midway through the sitting and exercise experimental conditions and again 5 minutes following the completion of the experimental conditions, peripheral blood glucose was assessed via a glucometer. If peripheral blood glucose fell below 70 mg/dL, testing was immediately discontinued for all measures. Following the peripheral blood glucose assessment, participants again completed the tests of inhibitory control and sustained attention while behavioral and neuroelectric measures were assessed. Finally, upon completion of the cognitive assessments, participants completed a symptom survey which assessed potential side effects of intranasal insulin that participants might have experienced at any time during the experimental protocol and if participants were still experiencing those symptoms.

Measures:

Safety of Intranasal Insulin: The safety of intranasal insulin in combination with exercise was assessed by examining the incidence of participants reporting potential side effects of intranasal insulin (Schmid et al., 2018) at any time during the experimental protocol and the persistence of those symptoms. Additionally, the extent to which peripheral blood glucose was altered was also assessed via glucometer at the beginning of the session, during the middle of the exercise/sitting condition, and following the exercise/sitting condition

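### Under the written day-2 order, a participant stopped early for safety does not reach the symptom survey, so Aims 1A and 1B would describe only those not stopped

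*Combined protocol and SAP*

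**What the plan says.** The Assessment day (day 2) section gives the order of events. Entry glucose is checked "to ensure that their blood glucose fell within the 70-115 mg/dL guideline to exercise safely", the pretest is done and the solution is given. Then: "Midway through the sitting and exercise experimental conditions and again 5 minutes following the completion of the experimental conditions, peripheral blood glucose was assessed". The stopping rule follows: "If peripheral blood glucose fell below 70 mg/dL, testing was immediately discontinued for all measures". The posttest comes next, and the survey is last: "Finally, upon completion of the cognitive assessments, participants completed a symptom survey which assessed potential side effects of intranasal insulin". It asks about symptoms at any time in the session and about those still present.

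The Abstract describes the instrument as a "symptom questionnaire assessing common symptoms of altered blood glucose and common side effects of intranasal insulin". Under Measures, Safety of Intranasal Insulin, reported side effects come first: "The safety of intranasal insulin in combination with exercise was assessed by examining the incidence of participants reporting potential side effects of intranasal insulin". The same paragraph adds the change in glucose across the three readings.

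Under Aims Assessment, item A of Aim 1 is the frequency of participants reporting any side effect, and item B the frequency with side effects persisting at the end. Item C is the frequency of discontinuations for safety reasons, with glucose outside 70 to 150 mg/dL, dizziness and inability to continue as examples. Items A and B state no denominator and no handling of a participant without a survey.

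**The concern.** Aim 1 is there "to ensure that undue risks are not incurred through combination therapeutic approaches". Its first two summaries rest on a survey that, in the written order, is reached only by participants who complete the posttest. Those who do not reach it are not a random subset, because a safety rule removed them. The low-glucose stop selects people whose glucose was altered, and symptoms of altered glucose are part of what the survey measures. A participant stopped for dizziness already has a symptom, yet by the written order would be counted in item C and not in item A. Item B is harder still, since persistence at the end is not defined for someone whose session ended early.

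If stops became more frequent with dose, the higher-dose groups would lose more of these participants. Their side-effect frequencies could then resemble placebo when the true frequencies differ. A reader could not detect this without the numbers dosed, stopped and surveyed in each group.

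**Working it through.** **The plan's own figure.** There is none to reproduce. The document states no group size, number of stops or symptom rate. Every input below is an assumption, except the 7 doses and 2 activities, which make 7 × 2 = 14 groups.

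**Step 1: the order of events.** Both post-dose glucose checks precede the posttest. A reading below 70 mg/dL ends testing. The survey follows completion of the posttest tasks. The text describes no survey or symptom record at a stop and no rule for a missing survey. So, as written, a stopped participant contributes nothing to items A and B.

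**Step 2: what else records these participants.** Item C counts the stop, including stops for dizziness. The triggering reading falls within the glucose-change measure. Neither gives the survey's full list of side effects or their persistence.

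**Step 3: range for one group.** Let n be the number dosed, s the number stopped without a survey, and r the number surveyed who report a side effect.

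- Among those surveyed: r/(n − s)
- Lower bound over all dosed: r/n
- Upper bound over all dosed: (r + s)/n
- Width: s/n

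With r = 1:

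| n | s | Surveyed only | Lower | Upper |
|---|---|---|---|---|
| 8 | 1 | 1/7 = 14.3% | 12.5% | 25.0% |
| 8 | 2 | 1/6 = 16.7% | 12.5% | 37.5% |
| 8 | 3 | 1/5 = 20.0% | 12.5% | 50.0% |
| 6 | 2 | 1/4 = 25.0% | 16.7% | 50.0% |
| 10 | 2 | 1/8 = 12.5% | 10.0% | 30.0% |

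The surveyed-only figure lies inside the range, so it can err in either direction. If d of the s stopped participants had a symptom noted at the stop, the lower bound for item A rises to (r + d)/n. With n = 8, s = 2, r = 1 and d = 1, the range becomes 2/8 = 25.0% to 3/8 = 37.5%.

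**Step 4: difference from placebo.** Let b be the side-effect rate among those not stopped and a the rate among those stopped, each the same in both groups. Let q be the stop probability on insulin and q0 that on 0 IU. The true frequency is qa + (1 − q)b on insulin and q0·a + (1 − q0)b on placebo. The expected surveyed-only frequency is b in both groups, so the expected surveyed-only difference is 0. The missed difference is therefore (q − q0)(a − b).

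With b = 0.20 and q0 = 0.02, in percentage points:

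| q | a = 0.10 | a = 0.20 | a = 0.50 | a = 0.90 |
|---|---|---|---|---|
| 0.05 | −0.3 | 0 | 0.9 | 2.1 |
| 0.10 | −0.8 | 0 | 2.4 | 5.6 |
| 0.30 | −2.8 | 0 | 8.4 | 19.6 |

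Check of one cell, q = 0.30 and a = 0.90: insulin 0.27 + 0.14 = 41.0%, placebo 0.018 + 0.196 = 21.4%, difference 19.6 points. The sign follows a − b when insulin raises the stop probability. A negative value is possible, because a participant stopped midway has had less time to develop symptoms.

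**The case against.** The strongest reply is that the day-2 section narrates a completed session and was not written to say what happens at a stop. A reader might infer that stopped participants actually went unsurveyed. The document does not say so. Staff may have given them the survey, and Figure 1, the diagram of the session, was not available for this review.

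Nor does the phrase about all measures settle it by pointing to the safety entry under Measures. That entry also includes the glucose readings, so the same reading would end glucose checks just when glucose was low. This objection stands against any claim about conduct. It does not remove the gap in the written order.

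A reader might also infer that these participants vanish from the safety data. They do not, given item C and the glucose-change measure. What is missing is their side-effect profile and its persistence.

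It is tempting to add that item C hides dose effects because no breakdown is stated. Items A and B state none either, and in a design built to ask about dose and activity, tabulation by group is the natural reading.

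Finally, the magnitudes are hypothetical, and nothing in the document supports stop probabilities as high as 0.30. A reading just below 70 mg/dL may cause no symptoms, since entry is allowed at 70. That argues for a range and against counting every stop as a side effect. The study is declared preliminary and too small for tests, but counts and ranges need no test.

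**Conclusion.** The point holds as a gap in the written procedure and in the definition of Aims 1A and 1B. Followed literally, the plan gives side-effect frequencies among participants who were not stopped, and the missing data are related to the safety outcome.

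The actual effect is unknown. It is zero if nobody was stopped or if every stopped participant was surveyed. The expected difference from placebo is also unaffected if the symptom rate is the same in stopped and other participants. Otherwise the range for a group is s/n wide, and the missed difference from placebo is (q − q0)(a − b), of either sign. On the assumed inputs above it runs from −2.8 to 19.6 points.

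A reader might infer that the survey result must flatter insulin. The document does not support that, because neither the stop rates nor the symptoms of stopped participants are given. The reporting change should be made; confidence is medium, because practice at a stop is not described.

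**What to change.** Data collection appears complete, since the text is in the past tense and reports achieved heart rates. The main change is therefore to reporting. For each of the 14 dose-by-activity groups, give:

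- the number dosed;
- the number stopped, by reason (glucose below 70, glucose above 150, dizziness, unable to continue);
- the number surveyed;
- items A and B among those surveyed;
- items A and B as a range over all dosed, counting stopped participants without a survey first as having no side effect and then as having one.

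Count any symptom recorded at the stop, such as dizziness, as an observed item A event. It does not by itself show persistence, so item B keeps its range for that participant. If stopped participants did complete the survey, say so and use those data; the range then narrows or closes.

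In any further conduct under this protocol, give the survey at the time of a stop as well as at the end.

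The cost is one table and a few sentences, drawn from glucose readings, stop records and surveys that the described procedures should have produced. The drawbacks are small cells, so counts and ranges only, and an upper bound that overstates harm if the stops were symptomless.

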- b. Participants must have normal or corrected-to-normal vision in order to complete the cognitive task.

Exclusion criteria: The following exclusion criteria exist for all participants:

- a. Lack of consent.
- b. Presence of any major neurological health issues, brain trauma, or concussion with loss of consciousness assessed through a health history and demographics questionnaire.
- c. Type I or Type II Diabetes.
- d. Self-reported pregnancy.
- e. Currently has any type of inflammation or blockage of the nasal passageways (i.e. allergies or a cold affecting the sinuses).
- f. Inability to engage in treadmill-based exercise.

Recruitment: Participants were recruited from the mid-Michigan community population via flyers and list-serve announcements.

Protocol: This investigation was approved by the Michigan State University Human Research Protection Program.

Screening Day (day 1): On the screening day of the testing protocol, following consenting to participate in this investigation; participants completed a brief health and history demographics questionnaire, a physical activity readiness questionnaire (Thomas et al., 1992), a medical screening questionnaire, the Wechsler Abbreviated Scale of Intelligence – 2nd Edition (WASI-II; (Wechsler, 2011), and a test of maximal oxygen uptake ($VO_2\text{max}$; using the same protocols as reported in (Chandler et al., 2019; Pontifex et al., 2016)). The medical screening questionnaire ensured that all participants were free of medication for high blood pressure, cholesterol, asthma, heart issues, depression/anxiety; and were not currently on any beta-blockers, sulfonamide antibiotics, corticosteroids, protease inhibitors, or Clonidine.

Participants who were eligible to continue in the study were then randomly assigned using a serial stratification approach accounting for biological sex to either an exercise [active experimental group] condition or sitting [control experimental group] condition. Within each condition; participants were subsequently randomly assigned using a serial stratification approach accounting for biological sex to receive a dose of either 0, 20, 40, 60, 80, 100, or 120 IU of fast acting insulin (Novolog Insulin Aspart 100 mg/mL) administered into the intranasal mucosa. Participants were instructed to refrain from exercise or caffeine intake, and too fast for at least 3 hours prior to participating in the second day of the testing protocol.

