Following removal of the eye blink components, stimulus-locked epochs were created for correct trials from -500 to 1,500 ms around the stimulus, baseline corrected using the -100 to 0 ms pre-stimulus period, and filtered using a zero phase shift low-pass filter at 30 Hz. Trials with artifact exceeding $\pm 100 \mu\text{V}$ were rejected. To ensure the integrity of the signal, stimulus-locked epochs were visually inspected blind to the experimental condition and dose prior to computing mean waveforms. Following visual inspection, the mean number of trials included in the waveforms was 112.0 [95% CI: 107.2 to 116.7] trials stimulus-locked to the congruent and incongruent trials (separately) of the Inhibitory Control task and 41.6 [95% CI: 40.1 to 43.2] trials stimulus-locked to the final stimulus of the target sequences of the Sustained Attention task.

Attention was indexed by the P3 ERP component. Attentional engagement was evaluated as the mean amplitude within a 50 ms interval surrounding the largest positive going peak within a 275 to 700 ms latency window following stimulus onset for the flanker task, and a 275 to 600 ms window for the RVIP task (Chandler et al., 2020; McGowan et al., 2019; Pontifex et al., 2015). Attentional processing speed was evaluated using ERP latency which was quantified as the time at which maximum peak amplitude occurred. Given the well-established nature of the P3 ERP component, analyses were conducted using a nine-channel region-of-interest approach centering around the topographic maxima of the P3 (i.e., the CP3/Z/4, P3/Z/4, PO5/Z/6 electrodes).

Aims Assessment:

- 1) *To provide a preliminary assessment of the safety profile of combining intranasal insulin with exercise; to ensure that undue risks are not incurred through combination therapeutic approaches.*

As the present investigation was a Phase II Clinical Trial, the research design is not sufficiently powered for hypothesis testing. Accordingly, this aim was satisfied by:

- A) Examining the frequency of participants reporting potential side effects of intranasal insulin at any time during the experimental protocol.
 - B) Examining the frequency of participants reporting potential side effects of intranasal insulin that persisted at the end of the experimental protocol.

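### The single end-of-session symptom survey has neither a baseline nor a post-dose window, so Aims 1A and 1B can count symptoms that began before dosing

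*Combined protocol and SAP*

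**What the plan says.** The Abstract describes a "symptom questionnaire assessing common symptoms of altered blood glucose and common side effects of intranasal insulin". Under Assessment day (day 2) it is given once, after the posttest: "Finally, upon completion of the cognitive assessments, participants completed a symptom survey". It covers "potential side effects of intranasal insulin that participants might have experienced at any time during the experimental protocol", and also asks whether those symptoms are still present.

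The Measures section (Safety of Intranasal Insulin) uses the same window, defining symptom safety as incidence "at any time during the experimental protocol and the persistence of those symptoms". Aims Assessment, Aim 1, item A uses it again: "Examining the frequency of participants reporting potential side effects of intranasal insulin at any time during the experimental protocol". Item B counts the symptoms that remained at the end.

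The term used for the window is also the label on the overview of day 2: "Figure 1. Diagram of experimental protocol". Dosing comes partway through that day: "Once the pretest cognitive assessment was completed, participants were administered solution into their intranasal mucosa". At screening, participants had been told to fast for at least 3 hours and to avoid caffeine and exercise beforehand. The only safety check described on day 2 before dosing is blood glucose.

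**The concern.** Efficacy is measured before and after dosing, and under Aim 2 it is corrected for the 0 IU group. Blood glucose is read at the start of the session, mid-condition and afterwards. The symptom survey has no first reading, its recall window does not start at dosing, and no rule on onset is given. A participant who already had a listed symptom on arrival, or developed one during the pretest, is eligible to be counted in 1A just like one whose symptom followed the sprays. If the symptom lasts, the participant is eligible for 1B as well.

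Items A and B are two of the three outputs that answer Aim 1. The questionnaire includes symptoms of altered blood glucose, and the participants were deliberately fasted, so some background reporting is plausible. Two things are at stake: whether the raw frequencies can be read as side effects, and how much of a real difference between doses or activities would show in them.

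**Working it through.** **Order of events.** The plan gives no symptom rate or sample size, so there is no figure to reproduce. The first check sets the survey window against the sequence of day 2 (Assessment day, Inhibitory Control Task, Sustained Attention Task):

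- Before the sprays: fasted arrival, glucose check, heart rate monitor, EEG preparation, flanker practice and test, sustained attention practice and test.
- After the sprays: 20 min of sitting or exercise with a mid-condition glucose check, a glucose check 5 min after the condition ends, both tasks again, then the survey.

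The plan uses a separate term, experimental condition, for the 20-minute sitting or exercise period. The survey's term is the one attached to the whole-day diagram, so the first list lies inside the window.

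**How much of the window precedes dosing.** Inputs from the documents: 80 + 160 = 240 flanker trials at pretest and 160 at posttest; mean inter-trial interval 2.5 s; 402 digits at 100 per minute = 4.02 min at each assessment; 1 min of sustained attention practice at pretest. A flanker trial is taken as 2.5 s if the interval runs onset to onset, or as 2.5 + 0.3 + 1.0 = 3.8 s if it is added to the flanker lead and response window.

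- Pre-dose at 2.5 s: 240 × 2.5/60 + 1 + 4.02 = 15.0 min. Post-dose: 20 + 5 + 160 × 2.5/60 + 4.02 = 35.7 min. Pre-dose share: 15.0/50.7 = 30%.
- Pre-dose at 3.8 s: 240 × 3.8/60 + 1 + 4.02 = 20.2 min. Post-dose: 20 + 5 + 160 × 3.8/60 + 4.02 = 39.2 min. Pre-dose share: 20.2/59.4 = 34%.

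EEG preparation is not timed in the documents. If it took 15 to 45 min (assumed), the pre-dose share would be about 46% to 63%.

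**Effect on the reported frequency.** Let b be the probability of a listed symptom before dosing and p the probability of one starting after dosing. If the two are independent, the any-symptom frequency reported under 1A is

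1 − (1 − b)(1 − p)

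and the reported difference between two groups is (1 − b)(p₂ − p₁). A participant already counted for a pre-dose symptom cannot be counted a second time. Since b is not given, a range is shown for assumed true post-dose rates of 10% and 30%, a 20-point difference:

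| b (assumed) | Reported, p = 10% | Reported, p = 30% | Reported difference |
|---|---|---|---|
| 5% | 1 − 0.95 × 0.90 = 14.5% | 1 − 0.95 × 0.70 = 33.5% | 19 points |
| 10% | 1 − 0.90 × 0.90 = 19% | 1 − 0.90 × 0.70 = 37% | 18 points |
| 20% | 1 − 0.80 × 0.90 = 28% | 1 − 0.80 × 0.70 = 44% | 16 points |
| 30% | 1 − 0.70 × 0.90 = 37% | 1 − 0.70 × 0.70 = 51% | 14 points |

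If treatment caused nothing (p = 0), the reported frequency would be b itself.

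**What subtracting 0 IU does.** The 0 IU group has the same b, so its subtraction removes the added background but leaves (1 − b)(p − p₀). At b = 30%, 51% − 37% = 14 points, not 20. Undoing the shrinkage would require b, which no described measurement supplies.

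**Per-symptom reporting.** The plan does not say whether frequencies are for any symptom or for each symptom. For a single symptom b would be smaller. At an assumed 2% to 5%, a 20-point difference becomes 0.98 × 20 = 19.6 to 0.95 × 20 = 19.0 points.

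**The case against.** The strongest reply is that the design already contains the control. Dose and activity are randomized, there is a 0 IU group in each activity condition, and every participant goes through the same pre-dose period. That stands. A reader might infer that the window biases the comparison towards some dose or activity, or towards finding no added risk. The documents do not support that: background symptoms are balanced in expectation, and the inflated raw rates overstate harm even as between-group differences shrink. What the reply does not remove is the shrinkage, or the fact that Aim 1 specifies only raw frequencies; placebo subtraction is stated only for Aim 2.

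Second, the questionnaire is not reproduced. A reader might infer that pre-dose symptoms were in fact counted. The documents show only that they are eligible. Someone asked about side effects might discount a symptom they arrived with. The exclusion of current nasal inflammation or blockage and the 70–115 mg/dL glucose check on arrival should also hold some background rates down.

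Third, a reader might infer that safety as a whole lacks a baseline. It does not: glucose has one, and item C (discontinuations) does not depend on the survey. The gap concerns symptoms only.

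Finally, Aim 1 is descriptive and the plan disclaims hypothesis testing. That limits the consequence. It does not make a raw frequency a treatment-emergent one.

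**Conclusion.** The point holds in a limited form. As written, the plan cannot separate symptoms that began before dosing from those that began after it, so 1A and 1B can include both. No arm is favoured in expectation. Raw any-symptom frequencies are raised by b(1 − p), and true differences are multiplied by (1 − b): a 20-point difference becomes 19 to 14 points for b between 5% and 30%, and hardly changes if symptoms are reported singly with b of 2% to 5%. These sizes rest on an assumed b and on independence of pre-dose and post-dose symptoms. How many pre-dose symptoms were actually counted cannot be known from the documents. This is a measurement weakness that is cheap to correct and, for data already in hand, a limitation to report; it does not invalidate the randomized comparison.

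**What to change.** **For further enrolment or a follow-on study.** Word the end-of-session survey to ask about symptoms since the nasal sprays were given and, for each one reported, whether it was present before the sprays. Alternatively, have participants complete the same form once just before the sprays. Define 1A as symptoms new or worse after dosing, and 1B as those of them still present at the end. State whether frequencies are for any symptom, for each symptom, or both. The cost is a change of wording, or a few minutes per participant for a second completion. Asking about symptoms before dosing may slightly prime later reports, equally in all arms. The recall item avoids that but relies on memory.

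**For data already collected.** The text is in the past tense and gives observed heart rates and trial counts, so a baseline probably cannot be added. Report 1A and 1B for each dose beside the 0 IU group in the same activity condition, with the difference from 0 IU. State that onset relative to dosing was not recorded, and that differences in any-symptom rates may therefore be understated. Do not describe the raw frequencies as side effects of the treatment. This needs one table and a sentence or two of text, with no new data.
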